Period 1 will begin at the Baseline Visit (Day 1) and will end at the Week 14 Visit. At the Baseline Visit, subjects who meet all the inclusion criteria and none of the exclusion criteria described in Section 5.2.1 and Section 5.2.2 will be enrolled into the study and randomized to double-blind treatment. During this period of the study, subjects will visit the study site at Weeks 2, 4, 8, 12, and 14. A ± 3 day window is permitted around scheduled study visits. The last dose of oral study drug in Period 1 is taken the day prior to the Week 14 visit.

Period 2 (90-Week Open-Label Extension Period)

Period 2 will begin at the Week 14 visit after all assessments have been completed. At Week 14, subjects on placebo will receive open-label upadacitinib 15 mg QD. Subjects on upadacitinib 15 mg QD will continue to receive the same treatment in an open-label manner. During Period 2, subjects will have a study visit at Weeks 16, 20, 24, 32, 40, 52, 64, 76, 88, 96, and 104. A ± 7 day window is permitted around scheduled study visits. Starting at Week 24, subjects who do not achieve at least an ASAS 20 response compared with Baseline at two consecutive visits will be discontinued from study drug treatment (see Section 5.4.1).

Discontinuation of Study Drug and Continuation of Study Participation

Subjects may discontinue study drug treatment, but may choose to continue to participate in the study (refer to Section 5.4.1 for additional details). Subjects who prematurely discontinue study drug should complete a Premature Discontinuation (PD) Visit as soon as possible, preferably within 2 weeks. Afterwards, subjects should follow the regular visit schedule and adhere to all study procedures except for dispensing study drug, pharmacokinetic (PK) sample collection, and blood sample collection for optional exploratory research and validation studies. In addition, future ASAS 20 nonresponse discontinuation criteria no longer apply. If at any point a subject no longer wants to provide assessments (withdrawal of informed consent) following discontinuation of study drug, a second PD visit is not required.

Premature Discontinuation of Study (Withdrawal of Informed Consent)

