- If a post-baseline urine pregnancy test is positive, study drug needs to be temporarily discontinued, and a serum pregnancy test is required. The serum pregnancy test will be sent to and performed by the central laboratory. If the serum pregnancy test is negative, study drug may be restarted. If the serum pregnancy test is positive, study drug must be permanently discontinued.

In Period 2, for women of childbearing potential, a urine pregnancy test will be performed at all visits and monthly at home between scheduled study visits. The results of the monthly at home tests will be communicated to the site. If a urine pregnancy test is positive, the subject must stop dosing, come in to the clinic, and have blood drawn for a serum pregnancy test that will be analyzed at the central laboratory.

At each visit, the study staff should review the pregnancy avoidance recommendations with each subject of childbearing potential and male subjects with a partner of childbearing potential and document this discussion in the subject's source records.

A pregnant or breastfeeding female will not be eligible for participation in this study or be allowed to continue study drug.

Clinical Laboratory Tests

Samples will be obtained for the clinical laboratory tests listed in [Table 2](#). Unscheduled clinical labs may be obtained at any time during the study if deemed appropriate per Investigator's discretion. A certified central laboratory will be utilized to process and provide results for the clinical laboratory tests. All abnormal laboratory tests that are considered clinically significant by the Investigator will be followed to a satisfactory resolution.

The central laboratory chosen for this study will provide instructions regarding the collection, processing, and shipping of these samples.

Blood samples will be obtained for the laboratory tests at visits specified in [Appendix E](#). Blood draws should be performed only after all clinical assessments, questionnaires, and vital sign determinations are obtained.

For clinic visits where samples for serum chemistry tests are collected, subjects should be fasting (a minimum 8-hour fast) whenever possible. If a subject is not able to fast when necessary due to unforeseen circumstances, the non-fasting status will be recorded in study source documentation.

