8.1.5 Safety Analysis

8.1.5.1 General Considerations

Safety analyses will be carried out using the Safety Analysis Set. Analyses will be conducted in primary analysis at Week 14, as well as for the entire study.

Safety analyses are based on treatments actually received. Safety will be assessed by treatment-emergent adverse events (TEAEs), physical examination, laboratory assessments, and vital signs. The number and percent of subjects experiencing TEAEs by treatment group will be tabulated by the Medical Dictionary for Drug Regulatory Activities (MedDRA[®]) system organ class (SOC) and preferred terms (PT). In addition,

summary of serious AEs and TEAEs by severity and relationship to study drug as assessed by the Investigators will be provided. SAEs, severe TEAEs, or TEAEs that lead to premature study discontinuation will be listed. The changes in vital signs, physical examination results, and clinical laboratory variables at each visit as compared to baseline will be summarized. Shift of laboratory values from baseline at defined time points will be tabulated.

Missing safety data will not be imputed.

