Appendix E. Study Activities

Activity	SCR (≤35D)	BL (D1)	Treatment Period																30 Day F/U Visit			
			Wk 2 D15	Wk 4 D29	Wk 8 D57	Wk 12 D85	Wk 14 D99	Wk 16 D113	Wk 20 D141	Wk 24 D169	Wk 32 D225	Wk 40 D281	Wk 52 D365	Wk 64 D449	Wk 76 D533	Wk 88 D617	Wk 96 D673	Wk 104 D729 /PD ^a				
Informed Consent	X																					
Inclusion/Exclusion Criteria	X	X ^b																				
Medical/Surgical History	X	X ^b																				
Alcohol and Nicotine Use	X							X								X					X	
Vital Signs/Weight/Height ^c	X ^c	X	X	X	X	X	X	X	X	X	X	X	X	X	X	X	X	X	X	X	X	X
Anterior Uveitis	X	X	X	X	X	X	X	X	X	X	X	X	X	X	X	X	X	X	X	X	X	X
Psoriasis		X	X	X	X	X	X	X	X	X	X	X	X	X	X	X	X	X	X	X	X	X
IBD		X	X	X	X	X	X	X	X	X	X	X	X	X	X	X	X	X	X	X	X	X
Physical Exam	X	X																				
12-Lead ECG	X ^d																					X
Chest X-Ray	X ^d																					X ^e
AP Pelvis X-Ray ^f	X																					
Lateral Cervical-Spine and Lateral Lumbar-Spine X-Ray ^f	X																					X

Activity	SCR (≤ 35D)	BL (D1)	Treatment Period														30 Day F/U Visit		
			Wk 2 D15	Wk 4 D29	Wk 8 D57	Wk 12 D85	Wk 14 D99	Wk 16 D113	Wk 20 D141	Wk 24 D169	Wk 32 D225	Wk 40 D281	Wk 52 D365	Wk 64 D449	Wk 76 D533	Wk 88 D617		Wk 96 D673	Wk 104 D729 /PD ^a
MRI of Spine and SI Joints ^g		X				X												X	
Low-Dose CT Scan of Spine ^h		X																X	
Latent TB risk assessment form	X ^d																	X ^e	
TB Screening (QuantiFERON-TB Gold test and/or PPD Skin Test)	X ^d																	X ^e	
Pregnancy Test	X ⁱ	X ^j	X ^j	X ^j	X ^j	X ^j	X ^j	X ^j	X ^j	X ^j	X ^j	X ^j	X ^j	X ^j	X ^j	X ^j	X ^j	X ^j	X ^j
Central lab tests Blood chemistry ^k Hematology Urinalysis ^l	X	X	X	X	X	X	X	X	X	X	X	X	X	X	X	X	X	X	X
Lymphocyte subsets		X						X										X	
ESR (local lab)	X	X	X	X	X	X	X	X	X	X	X	X	X	X	X	X	X	X	X
FSH ^m	X																		
HBV/HCV ⁿ	X						X ^o								X ^o	X ^o	X ^o	X ^o	X ^o
HIV ^p	X																		
HLA-B27 ^{q,r}		X																	
hsCRP ^s	X	X	X	X	X	X	X	X	X	X	X	X	X	X	X	X	X	X	X

Activity	SCR (≤ 35D)	BL (D1)	Treatment Period															30 Day F/U Visit			
			Wk 2 D15	Wk 4 D29	Wk 8 D57	Wk 12 D85	Wk 14 D99	Wk 16 D113	Wk 20 D141	Wk 24 D169	Wk 32 D225	Wk 40 D281	Wk 52 D365	Wk 64 D449	Wk 76 D533	Wk 88 D617	Wk 96 D673		Wk 104 D729 /PD ^a		

█ samples for exploratory research and validation studies (optional – see Appendix F)^t
			X ^u	X ^u	X ^v	X ^v	X ^v	X ^v													
Blood samples for upadacitinib PK assay			X	X	X	X	X	X						X ^v					X ^v		

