5.2 Analysis Windows

Definition of Study Days (Days Relative to the First Dose of Study Drug)

Study Days are calculated for each collection date relative to the date of the first dose of study drug. It is defined as the number of days between the date of the first dose of study drug and the collection date. Study days are negative values when the collection date of interest is prior to the first study drug dose date. Study days are positive values when the collection date of interest is on or after the first study drug dose date. The day of the

first dose of study drug is defined as Study Day 1, while the day prior to the first study drug dose is defined as Study Day –1 (there is no Study Day 0). Study days are used to map actual study visits to the protocol-specified study visits.

Definition of Analysis Windows

The following rules will be applied to assign actual subject visits to protocol-specified visits. For each protocol-specified study visit, a target study day will be identified to represent the corresponding visit along with a window around the target day. Windows will be selected in a non-overlapping fashion so that a collection date does not fall into multiple visit windows. If a subject has two or more actual visits in one visit window, the visit closest to the target day will be used for analysis. If two visits are equidistant from the target day, then the later visit will be used for analysis.

The visit window and the target study day for each protocol-specified visit in Period 1 are displayed in [Table 1](#) and [Table 3](#) (depending on the different visit schedules of different endpoints). Visit windows for protocol-specified visits in Period 2 are defined similarly.

Table 1. Analysis Windows for Efficacy Analysis for Period 1 (for ASAS Components, BASDAI, BASFI and ASDAS components) and Safety Analysis of Vital Signs for Period 1

Protocol Specified Visit Week	Lower Bound	Target Day	Upper Bound
Baseline	–99	1 ^a	1
2	2	15	22
4	23	29	43
8	44	57	71
12	72	85	92
14	93	99	First dose date of Period 2

a. Day of first dose of study drug.

Table 2. Analysis Windows for Safety Analysis of lab values for Period 1

Protocol Specified Visit Week	Lower Bound	Target Day	Upper Bound
Baseline	-99	1 ^a	1
4	2	29	43
8	44	57	71
12	72	85	92
14	93	99	First dose date of Period 2

a. Day of first dose of study drug.

Table 3. Analysis Windows for Efficacy Analysis for Period 1 (for ASAS HI)

Protocol Specified Visit Week	Lower Bound	Target Day	Upper Bound

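### The SAP's Period 1 lab windows have no Week 2 row although Appendix E appears to schedule a Week 2 draw, so Week 2 labs drop out of the by-visit summaries and the ANOVA, or are labelled Week 4

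*SAP*

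**What the plan says.** Protocol 5.1 sets the Period 1 schedule: "subjects will visit the study site at Weeks 2, 4, 8, 12, and 14", with a window of plus or minus 3 days. Protocol 5.3.1.1 leaves the lab schedule to the activity grid ("Blood samples will be obtained for the laboratory tests at visits specified in" Appendix E). The grid row beginning "Central lab tests Blood chemistry", which also covers hematology and urinalysis, carries a mark in every column, Week 2 (Day 15) among them. For the analysis, protocol 8.1.5.1 states that changes in "clinical laboratory variables at each visit as compared to baseline will be summarized".

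SAP 5.2 has a separate table for labs, "Table 2. Analysis Windows for Safety Analysis of lab values for Period 1". Its post-baseline rows are Week 4 (Days 2 to 43, target 29), Week 8 (44 to 71, target 57), Week 12 (72 to 92, target 85) and Week 14 (from Day 93, target 99). SAP Table 1, which covers vital signs and the ASDAS components among others, does have a Week 2 row (Days 2 to 22, target 15) and starts Week 4 at Day 23. For duplicates, SAP 5.2 says: "If a subject has two or more actual visits in one visit window, the visit closest to the target day will be used for analysis". SAP 10.3.2.1 then summarises labs by visit and treatment group, and adds an ANOVA against placebo on change and percent change for ten selected parameters.

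**The concern.** If labs are drawn at Week 2, the SAP has nowhere to put them. They fall in the Week 4 window and are either set aside or presented under the wrong visit. Week 2 is the first on-treatment sample, and it lies in the only placebo-controlled period. The ANOVA parameters (hemoglobin, platelets, lymphocytes, neutrophils, creatinine, CPK, LDL, HDL, LDL/HDL ratio and total cholesterol) are those the SAP singles out as of clinical interest. As written, no by-visit mean change and no between-arm difference can be produced for any of them before Week 4. The Week 4 figures can also mix two-week and four-week exposure, because a subject with no Week 4 sample contributes a Week 2 value.

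**Working it through.** **1. Is a Week 2 draw scheduled?** The grid columns are Screening, Baseline, sixteen post-baseline visits (Weeks 2, 4, 8, 12, 14, 16, 20, 24, 32, 40, 52, 64, 76, 88, 96, 104/PD) and follow-up: 2 + 16 + 1 = 19. The safety-lab row has 19 marks, so no column is left blank. Two rows in the same part of the grid show the same pattern and can be checked elsewhere:
- Pregnancy tests: the prose of protocol 5.3.1.1 places them at every visit.
- hsCRP: it is an ASDAS component (SAP 9.4.1), and SAP Table 1 gives those components a Week 2 window. SAP Table 10 also lists hs-CRP as a laboratory variable, so the SAP already windows one central-lab blood test at Week 2.

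**2. Reproduce the SAP windows.** Rule: upper bound = midpoint between adjacent targets; lower bound = previous upper bound + 1; first post-baseline lower bound = Day 2.
- Targets 29, 57, 85, 99: (29 + 57)/2 = 43; (57 + 85)/2 = 71; (85 + 99)/2 = 92. Windows 2–43, 44–71, 72–92, 93 onward. This is Table 2 exactly.
- Adding target 15: (15 + 29)/2 = 22. Windows 2–22, 23–43, and the rest unchanged. This is Table 1 exactly.

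The two tables differ only in the Week 2 target.

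**3. Apply the duplicate rule under Table 2.** Distance = |study day − 29|. With the ±3-day visit window:

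| Sample | Study days | Distance from Day 29 |
|---|---|---|
| Week 2 | 12 to 18 | 17 down to 11 |
| Week 4 | 26 to 32 | 0 to 3 |

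The smallest Week 2 distance (11) exceeds the largest Week 4 distance (3), so Week 4 is kept for every in-window pair.

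**4. Other cases.**
- No Week 4 sample: the Week 2 value is the only one in Days 2 to 43 and is reported as Week 4. A Day 15 value is 14 days before the target.
- Very late Week 4 sample: Day 43 is 14 days from target and a Day 16 sample is 13, so the Week 2 value displaces it. This needs a Week 4 visit well outside the protocol window.

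**5. Size.** Post-baseline Period 1 lab visits: 5 (Weeks 2, 4, 8, 12, 14). Lost to by-visit analysis: 1, so 1/5 = 20%. If all of the planned 170 subjects gave a Week 2 sample, that is up to about 170 sample sets.

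**6. What is not lost.** SAP 10.3.2.2 (minimum and maximum shifts), 10.3.2.3 (Grade 3 or higher) and 10.3.2.4 (liver elevations) are not defined by visit. Nothing in those sections confines them to the record selected for a window, so an extreme Week 2 value can still be counted there.

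**The case against.** The strongest objection is that the Week 2 draw rests on a grid that is visibly broken in the text copy. No sentence says chemistry, hematology or urinalysis is taken at Week 2. The Period 1 follow-up MRI mark sits under Week 12 although the prose says Week 14; the CT row lacks Week 52; the PK marks do not match the listed weeks; the vital-signs row has 22 marks for 19 columns; and the AS QoL row shows Weeks 2 and 12, which SAP Table 4 does not have. The SAP also says that windows follow each endpoint's own schedule, and Table 2 is exactly what a 4/8/12/14 schedule would give. This stands in part. A full row of 19 marks cannot come from dropped blanks or a column shift, and the hsCRP and pregnancy rows support the reading, but the source PDF must settle it. If Week 2 is blank there, Table 2 is consistent and the point falls.

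Four stronger readings are tempting and are not supported:
- That early lab toxicity vanishes from the safety analysis. The outputs in step 6 can still capture it, and an external DMC reviewed unblinded safety data.
- That the omission is peculiar to labs. SAP Table 4 (AS QoL and MASES) also has no Week 2 row and gives Days 2 to 43 to Week 4.
- That it bears on the pausing rules in protocol Table 4. Those act on individual confirmed results during conduct, not on visit means, and that table has no lipid rule.
- That correction is free of any downside. SAP section 11 dates the Week 14 lock to February 2019, so changing Period 1 windows now is a post-lock step.

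**Conclusion.** On the grid as it reads, the protocol and SAP do not agree: labs are scheduled at Week 2 and promised at each visit, and the SAP cannot report them at that visit or give a reason for leaving them out. The effect is moderate and confined to safety: one of five controlled lab visits is absent from the by-visit means and the ANOVA in SAP 10.3.2.1, and a Week 2 value is mislabelled whenever the Week 4 sample is missing. How often that happens cannot be derived from the documents. The primary endpoint, the ranked secondary endpoints and the type I error are unaffected. The conclusion assumes that the Week 2 mark is present in the source PDF; the statement that Week 2 never wins assumes both visits fall within ±3 days.

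**What to change.** First confirm the Week 2 mark for chemistry, hematology and urinalysis in the source PDF of Appendix E. If it is there:
- Add a Week 2 row to SAP Table 2 (Days 2 to 22, target 15) and start Week 4 at Day 23, as Table 1 does. Later rows stay as they are.
- Report the 10.3.2.1 lab change and between-arm difference at Week 2 as a supplementary Period 1 output, labelled as added after the Week 14 lock.
- Use the same windows in the by-visit lab summaries of SAP 10.3.3.1 at the Week 104 lock, so that the gap is not carried forward.

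If Week 2 labs were left out on purpose, state the reason in SAP 5.2. The cost is one added row, one changed bound and a supplementary run on data already collected. The small downside is that the run comes after the Period 1 lock, which the labelling makes plain.

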X-rays will be sent to the central imaging laboratory designated by the Sponsor. Digitalized images are acceptable, provided that they meet the specifications outlined in the IAG/Site Operations Manual. X-rays not meeting the quality requirements must be repeated within the 35-day screening window. The AP pelvis x-ray will be read by the central imaging vendor solely to evaluate the SI joints for the presence of sacroiliitis consistent with AS based on the modified New York Criteria for AS, while the x-rays of the spine will be read by the central imaging vendor only for the purposes of scoring for radiographic progression. Subjects can only receive first dose of study drug after the x-rays have been centrally read and sacroiliitis is confirmed.

Screening x-rays of spine and pelvis will serve as baseline x-rays for scoring purposes.

Handling of X-rays of Spine after Baseline

X-rays of the spine will be obtained at the Week 104 Visit (end of study). If a subject prematurely discontinues the study and/or study drug, depending on the time of discontinuation, new x-rays of the spine may be needed.

- Subjects who prematurely discontinue from the study and/or study drug before Week 76 will not have x-rays performed at the PD Visit.
 - If the subject continues study participation, the subject will follow the regular visit schedule, and an x-ray will be performed at the Week 104 Visit.
- Subjects who prematurely discontinue from the study and/or study drug at or after Week 76 will have x-rays performed at the PD Visit.
 - If the subject continues study participation, the subject will follow the regular visit schedule, but an x-ray will not be performed at the Week 104 Visit.

The x-rays of the spine will be read by the central imaging vendor only for the purposes of scoring for radiographic progression.

MRI of Spine and SI Joints

All subjects who meet eligibility criteria will have an MRI evaluation of the SI joints, as well as the cervical, thoracic, and lumbar regions of the spine, prior to or at the Baseline Visit, the Week 14 Visit, as well as the Week 104 Visit. If a site is unable to obtain the MRI prior to Baseline Visit, a window of 3 days post-dose will be allowed. For the MRI at Week 14, a window of -7 days/+ 3 days will be allowed; for the MRI at Week 104, a window of ± 7 days will be allowed. If subject has a contraindication for MRI prior to enrollment, the site must discuss with the AbbVie TA MD.

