- a. Subjects who prematurely discontinue the study or study drug should complete the procedures outlined in the PD Visit within 2 weeks of last dose of study drug and preferably prior to the administration of new therapies.
 - b. Update Inclusion/Exclusion, prior and concomitant therapy, and Medical/Surgical History to prior to enrollment to assure subject eligibility.
 - c. Height will be measured at Screening Visit only.
 - d. These procedures will not be required if the subject had a previous normal ECG, normal CXR, or negative TB test within 90 days of Screening, provided all protocol-required documentation is available at the site and nothing has changed in the subjects health status since the time of the test that warrants a repeat test. Any documentation of past positive PPD or IGRA results may be acceptable; however, negative PPD or IGRA test done more than 90 days prior to the Screening Visit will need to be repeated. If the subject has a positive PPD test or IGRA test, has had a past ulcerative reaction to PPD placement, and/or a CXR consistent with prior TB exposure, the subject will be required to have documented completion of a full course of TB prophylaxis prior to the Baseline Visit.
Refer to Section 5.3.1.1. Study Procedures, TB Testing for specific requirements for TB testing and TB prophylaxis.
 - e. Obtain chest x-ray for subjects with TB risk factors as identified by the TB risk assessment form for subjects living in areas endemic for TB or for subjects with a newly-positive QuantiferON-TB Gold test (and/or PPD skin test) after baseline. Refer to Section 5.3.1.1, Study Procedures, TB Testing for specific requirements for TB testing and TB Prophylaxis.
 - f. X-rays of the spine and pelvis will not be required during the Screening Period if the subject had a previous anteroposterior pelvis x-ray and lateral spine x rays within 90 days of the Screening Period, provided that the x-rays are confirmed to be adequate for the required evaluations and are deemed acceptable by the central imaging vendor.
 - g. MRI should be performed prior to or at Baseline in subjects who meet eligibility criteria, and at Week 14 and Week 104. If subject has a contraindication for MRI prior to enrollment, site must discuss with the AbbVie TA MD. If a site is unable to obtain the MRI prior to Baseline, a window of 3 days post-dose will be allowed.

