Baseline	-99	1 ^a	1
2	2	15	22
4	23	29	43
8	44	57	78
14	79	99	First dose date of Period 2

a. Day of first dose of study drug.

Table 4. Analysis Windows for Efficacy Analysis for Period 1 (for AS QoL and MASES)

Protocol Specified Visit Week	Lower Bound	Target Day	Upper Bound
Baseline	-99	1 ^a	1
4	2	29	43
8	44	57	78
14	79	99	First dose date of Period 2

a. Day of first dose of study drug.

Table 5. Analysis Windows for Efficacy Analysis for Period 1 (for FACIT-F, ISI, WPAI, BASMI, TJC/SJC and Dactylitis)

Protocol Specified Visit Week	Lower Bound	Target Day	Upper Bound
Baseline	-99	1 ^a	1
14	2	99	First dose date of Period 2

a. Day of first dose of study drug.

Table 6. Analysis Windows for Efficacy Analysis for Period 1 (for MRI joints and spine SPARCC)

Protocol Specified Visit Week	Lower Bound	Target Day	Upper Bound
Baseline	-99	1 ^a	3
14	4	99	First dose date of Period 2

a. Day of first dose of study drug.

If first dose date of Period 2 is missing, the Upper Bound of Week 14 will be set at Day 106, which is half way of Week 14 and next visit Week 16.

6.0 Demographics, Baseline Characteristics, Medical History, and Previous/Concomitant Medications

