9.2.3 Key Secondary Efficacy Analyses

The key multiplicity adjusted secondary efficacy endpoints at Week 14 are:

1. Change from Baseline in Ankylosing Spondylitis Disease Activity Score (ASDAS(CRP));
2. Change from Baseline in MRI Spondyloarthritis Research Consortium of Canada (SPARCC) score (Spine);

3. Proportion of subjects with BASDAI 50 response (defined as 50% improvement in the Bath AS Disease Activity Index);
4. Change from Baseline in AS QoL;
5. Proportion of subjects with ASAS partial remission (PR) (defined as an absolute score of ≤ 2 units for each of the four domains identified in ASAS 40);
6. Change from Baseline in BASFI;
7. Change from Baseline in BASMI_{lin};
8. Change from Baseline in MASES (for subjects with baseline enthesitis);
9. Change from Baseline in WPAI (the overall work impairment due to SpA);
10. Change from Baseline in ASAS HI.

Additional key secondary endpoints are:

- ASAS 20 response at Week 14.
- Change from Baseline in MRI SPARCC score (SI joints) at Week 14.

For binary endpoints, frequencies and percentages will be reported for each randomized treatment group. The primary estimand is the same as that for the primary efficacy endpoint as defined in Section 9.2.1, except for the definition of the efficacy measurement. NRI data handling will be used to analyze the primary estimand.

Supplementary analysis using AO data handling will also be conducted. The corresponding supplementary estimand is the same as defined in Section 9.2.2 except for the definition of the efficacy measurement. To explore various missing data assumptions including missing not at random (MNAR), tipping point analysis will also be conducted for ASAS 20 at Week 14 and details of the analysis are outlined in Appendix E.

Point estimate and 95% CI using normal approximation will be provided for the response rate for each randomized treatment group. Treatment comparisons will be made between

upadacitinib and the placebo group using the Cochran-Mantel-Haenszel. The CMH test adjusts for the main stratification factor of hsCRP level (\leq ULN vs. $>$ ULN). Point estimate, 95% CI using normal approximation and the p-value for the treatment difference will be presented.

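### The SAP's MRI baseline window closes one study day before the protocol's 3-day post-dose allowance, so a permitted Day 4 baseline scan is assigned to Week 14

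*SAP*

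**What the plan says.** **Protocol.** Section 5.3.1.1 (MRI of Spine and SI Joints) asks for the first MRI before or at the Baseline Visit, with one exception: "If a site is unable to obtain the MRI prior to Baseline Visit, a window of 3 days post-dose will be allowed". Appendix E, note g, repeats it: "If a site is unable to obtain the MRI prior to Baseline, a window of 3 days post-dose will be allowed".

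**SAP Section 5.2, study day.** The day of the "first dose of study drug is defined as Study Day 1", and "there is no Study Day 0". The same paragraph opens with a looser description of study day: "It is defined as the number of days between the date of the first dose of study drug and the collection date". Study day is then used to map actual visits to protocol visits.

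**SAP Section 5.2, Table 6.** The table is headed "Table 6. Analysis Windows for Efficacy Analysis for Period 1 (for MRI joints and spine SPARCC"). For MRI SPARCC, Baseline runs from Day -99 to Day 3 (target Day 1). Week 14 runs from Day 4 to the first dose date of Period 2 (target Day 99). If two scans fall in one window, "the visit closest to the target day will be used for analysis". Section 5.2 has no rule that lets the nominal visit label override the study day.

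**SAP Section 9.2.3.** Change from baseline in SPARCC spine at Week 14 is second in the list of multiplicity-adjusted secondary endpoints. The SI-joint score is an additional key secondary endpoint: "Change from Baseline in MRI SPARCC score (SI joints) at Week 14".

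**The concern.** Tables 1 to 5 of SAP Section 5.2 end Baseline at Day 1; only the MRI table goes to Day 3. The only provision that matches this extension is the protocol's 3-day allowance. The bound therefore seems meant to carry that allowance into the analysis, and under the SAP's own day numbering it falls one day short.

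The protocol permits a post-dose scan only when the site could not obtain one earlier, so a Day 4 scan will normally be the subject's only baseline image. If Table 6 is applied as written, that subject has no baseline SPARCC value. The model in SAP Appendix D needs both the change score and the baseline value, and Table 6 has a single post-baseline visit, so no other visit keeps the subject in the MMRM. The supplementary ANCOVA on observed data also needs the baseline. The subject drops out of both analyses for both SPARCC scores, and out of the baseline SPARCC summaries.

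**Working it through.** **Inputs**

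- Allowance: up to 3 days after the first dose (Protocol 5.3.1.1; Appendix E, note g).
- Day numbering: dosing day is Day 1, no Day 0 (SAP 5.2).
- Windows: Baseline -99 to 3; Week 14 from 4, target 99 (SAP Table 6).

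**Step 1. Confirm the numbering.** For dates on or after the first dose, study day = (collection date - first dose date) + 1. A visit at week w then falls on 1 + 7w. Weeks 2, 4, 8, 12 and 14 give 15, 29, 57, 85 and 99, which are the target days in SAP Table 1. Weeks 16, 52 and 104 give 113, 365 and 729. All eight match Protocol Appendix E.

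**Step 2. Try to reproduce the stated bound of 3.**

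- SAP numbering: 1 + 3 = Day 4. This does not give 3.
- Plain date difference: 3. This makes the dosing day Day 0, which the SAP excludes, and Week 14 would be Day 98, not 99.
- Counting the dosing day as the first of the three days: Day 3. This is not the ordinary meaning of three days after a dose.

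**Step 3. Map each permitted scan date from the dosing day onward.**

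| Days after first dose | Study day | Table 6 as written | Bounds moved to 4 and 5 |
|---|---|---|---|
| 0 | 1 | Baseline | Baseline |
| 1 | 2 | Baseline | Baseline |
| 2 | 3 | Baseline | Baseline |
| 3 | 4 | Week 14 | Baseline |

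**Step 4. Follow a Day 4 scan through the rules.** Its distance from the Week 14 target is 99 - 4 = 95 days. If the subject also has a scan near Day 99, that scan is selected and the Day 4 scan goes unused. If there is no later scan in the window, the Day 4 scan becomes the Week 14 value. If it was the only baseline scan, neither case yields a change score.

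**Step 5. Size, by illustration only.** Take 170 x 0.9 = 153 evaluable subjects. This borrows the dropout assumption of the ASAS 40 sample-size calculation and is not a count of MRI-evaluable subjects. Losing k subjects multiplies the standard error by 1/sqrt(1 - k/153). The documents state no power for SPARCC. If it were 90%, it would become Phi(3.2415 x sqrt(1 - k/153) - 1.96), where 3.2415 is the sum of the normal quantiles for two-sided 0.05 and 90% power.

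| k lost | SE factor | Power if 90% before |
|---|---|---|
| 1 | 1.0033 | 89.8% |
| 2 | 1.0066 | 89.6% |
| 3 | 1.0100 | 89.4% |
| 5 | 1.0168 | 89.0% |

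**The case against.** The arithmetic is hard to dispute; the case on the other side concerns reach.

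- **Missing data, not contamination.** A Day 4 image can enter a Week 14 change score only if the subject also has an earlier baseline scan and no later Week 14 scan. Otherwise the subject is simply lost. Labelling depends on scan date under blinded treatment, so the documents give no reason to expect a difference between arms. This stands.
- **Few scans, perhaps none.** Day 4 is one of four dates from the dosing day onward, but one of up to 39 if the 35-day screening period is counted (35 + 4). Neither ratio is a frequency. This stands.
- **The power figures are hypothetical.** The numbers lost, the 90% and the 153 are all assumed. This stands; their only use is to show that the effect is small.
- **The protocol does not state its allowance as a study day, and the SAP's opening description of study day yields 3.** This may explain how the bound arose, but it does not rescue it: the same paragraph fixes the dosing day as Day 1, and every target day agrees with that. If the sponsor meant to count the dosing day, the SAP should say so.
- **Week 104.** Table 6 is for Period 1, and SAP Section 5.2 says only that Period 2 windows are defined in a similar way. That Week 104 uses the same MRI baseline is a reasonable inference, not a stated rule. Changing the bound now would also follow the unblinded Week 14 analysis. Both cautions stand, but Section 9.1.1 plans no testing for long-term efficacy.

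**Conclusion.** The concern holds, as a minor point. Under the SAP's own numbering the Table 6 baseline bound is one day short of the protocol's allowance, and a permitted Day 4 scan is assigned to Week 14. A subject whose only baseline scan was on that day is lost from the SPARCC spine and SI-joint comparisons. Confidence in the mismatch is high; confidence that any scan is affected is low, because the documents give no scan dates. In the illustration, losing 1 to 5 of 153 subjects raises the standard error by 0.3% to 1.7% and lowers an assumed 90% power by at most 1 point. The primary endpoint, alpha and the sample size are not affected.

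One related point needs reconciling only. The protocol's Week 14 MRI window of -7 to +3 days could run past the Table 6 upper bound if Period 2 dosing started before the scan. Protocol Section 5.1 implies that it should not, since Period 2 starts after the Week 14 assessments are complete. The bound also serves a purpose: it keeps open-label drug out of the placebo comparison.

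**What to change.** 1. In SAP Table 6, set the Baseline upper bound to Day 4 and the Week 14 lower bound to Day 5.
2. In SAP Section 5.2, define study day as collection date minus first dose date plus 1 for dates on or after the first dose.
3. SAP Section 11.0 records that the Week 14 lock was completed in February 2019. Keep the locked result and report, by arm, how many scans change label. If the count is zero, the matter is closed. If not, show the corrected Week 14 SPARCC spine and SI-joint results as supportive.
4. Use the corrected bound for the Week 104 MRI analysis and state that it uses the same MRI baseline. If any scan moves, note that the Week 104 baseline set differs from the locked Week 14 set and that the change was made after unblinding.
5. Keep the existing Week 14 upper bound for the main analysis and report, by arm, how many protocol-compliant Week 14 scans it excludes, if any.

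The cost is very low: two numbers in one table, one sentence on study day, a statement of the Week 104 baseline and two counts by arm, with a supportive table only if a scan changes label. The drawback is that any relabelling follows the unblinded Week 14 analysis, so it cannot replace the locked Week 14 result.
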